1.0 PROTOCOL TITLE: Evaluation of biomarkers for predicting macronutrient intake

Protocol Version Date: 10/26/2023

Check if this research has U.S. Federal government funding via one or more direct awards or a sub-award. Provide the source of federal support: National Institutes of Health

All other sources of funding:

2.0 PRINCIPAL INVESTIGATOR:

[name], PhD. Professor, Ponder Endowed Chair. Physician Nutrition Specialist. Editor-in-Chief Clinical Nutrition and e-SPEN Journal. Director Center for Translational Research in Aging & Longevity.

3.0 Co- INVESTIGATORS:

[name]. [name] [name] in Biomedical Engineering. Head, Department of Biomedical Engineering. Faculty, Department of Materials Science and Engineering. Center for Remote Health Technologies and Systems.

[name]. Professor, Head Clinical Research. Co-director Center for Translational Research in Aging & Longevity.

4.0 Objectives:

Establish a quantitative relationship between macronutrient intake from fresh meals and the resulting blood and ISF levels of small-molecule metabolites (nutritional biomarkers)

5.0 Background:

Introduction

The increase in plasma concentration of glucose and amino acids (AAs) is directly related to the amount of carbohydrates and protein/free AAs consumed, respectively. However, while glucose dynamics have been studied intensely, the relationship between protein intake and AA levels in ISF is less understood and more complex. Our preliminary results show a different plasma-ISF relationship for individual AAs, with only a few exhibiting strong enough relationships to use ISF levels in predicting plasma levels for liquid meals. It is also unclear whether the ISF concentration is a valid proxy when solid meals are consumed. Therefore, a controlled study with healthy part will be conducted to establish quantitative relationships between compartmental concentrations of macronutrients and metabolites. This study will evaluate the effects of meal composition (macronutrient intake) on the levels of metabolites in blood and interstitial fluid.

Significance

Monitoring and optimizing dietary intake are important for precision nutrition in the treatment of clinical conditions (diabetes, obesity, kidney/liver failure, etc) as well as attenuating loss of muscle function and mass during aging. Processing of macronutrients (carbohydrates, protein, and fat) is believed to be highly personalized. Unfortunately, current methods for personal

IRB NUMBER: IRB2023-0400F

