- Known allergy or intolerance to any of the meal components
- Any other condition according to the PI or nurse that was found during the screening visit, that would interfere with the study or safety of the patient
- Failure to give informed consent or Investigator's uncertainty about the willingness or ability of the participant to comply with the protocol requirements

When during the period from enrollment to completion of the study any condition is developed, whether causing the participant to not meet inclusion criteria or to meet exclusion criteria, they will be excluded from the study.

7.0 Number of Local Participants:

IRB NUMBER: IRB2023-0400F
IRB APPROVAL DATE: 4/10/2024

Up to 40 individuals will be enrolled in the study. For establishing the quantitative relationship between macronutrient food intake and resulting plasma and ISF values of small molecule markers (Aim 1), our initial focus will be on classical time-series techniques, which can operate well with limited training data. Based on a sample size calculation for the machine-learning model to distinguish a 30% difference in protein and CHO amounts with power of 0.8 and significance level of 0.05, we will need 33 healthy participants, 8 meals per participant. Estimating 20% dropout.

8.0 Study-Wide Number of Participants:

n/a

9.0 Study Timelines:

1 screening visit ~2 hours

4 study visits each ~15 hours over the course of 3-6 weeks

Total time: ~62 hours

10.0 Study Endpoints:

Primary Endpoint

- Prediction models of postprandial plasma glucose in relation to the macronutrient content of predefined meals as assessed by plasma and/or ISF concentrations of amino acids, glucose, and/or triglycerides

11.0 Procedures Involved:

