The study will take place at the research facility of the Center for Translational Research on Aging and Longevity (CTRAL), Texas A&M University located in the Human Clinical Research Building. The study involves 1 screening visit lasting up to 2 hours and fasting prior to screening is not required. We will screen participants for any disease or condition that could interfere with the studies. We also will perform Dual-energy X-ray absorptiometry (DXA) to measure body composition. We will also ask participants to answer demographic questions, questions about general health and nutrition, eating habits, etc. Demographic characteristics will be collected at baseline. Prior to completion of the study, all participants will also complete a series of questionnaires. Questionnaires are used to assess the current cognitive and mental well-being. Questionnaires, such as the following, may be completed during the study days:

- 3-day food diary to determine habitual dietary intake
- Questionnaire about gut function and symptoms: The Gastrointestinal Symptom Rating Scale (GSRS)
- Questionnaire about activity: Physical Activity Scale for the Elderly (PASE) & Baeck
- Questionnaires about general well-being: Sf36

On each study day, body weight will be measured. Participants will be fed up to 8 different meals (see **Table 1**) with specific nutritional composition (two per day) and then monitored for four hours after the meal. Meals will be spaced at 8 hours to limit overlapping effects. Meal sets will be randomized across study days (see **Table 2**). At the end of the second monitoring period, catheters will be removed and participants will be given an additional meal. Participants will be able to go to the restroom and drink water ad libitum throughout each study day. See **Figure 1** for an overview of the study day. The microdialysis pump which contains the perfuse solution and catheters will be securely affixed to the subjects forearm using coban. See **Figure 2** for a schematic picture of the microdialysis setup and an actual photo of the pump used by CTRAL. This will ensure maintenance of proper placement and collection of samples while out of the

IRB NUMBER: IRB2023-0400F
IRB APPROVAL DATE: 4/10/2024

bed. Participants will return 3 times (4 total study days per participant), where the same procedure will be repeated with meals of different compositions.

Table 1. Type and composition of study meals

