Meal Number	Carbohydrate (g)	Protein (g)	Fat (g)	Energy (kcal)
1	40	15	15	355
2	40	15	40	580
3	180	40	15	1015
4	180	40	40	1240
5	180	15	15	915
6	40	40	15	455
7	180	15	40	1140
8	40	40	40	680

All meals will be prepared by a local company ([Heat Ups](#)) to match the composition of the Frozen Meals.

Table 2. Meal sets to be randomized across the study day

	AM Meal	PM Meal	Total Calories (kcal)
Meal set A	Meal 1	Meal 4	1595
Meal set B	Meal 6	Meal 7	1595
Meal set C	Meal 2	Meal 3	1595
Meal set D	Meal 5	Meal 8	1595

Meal sets will be randomized across study days for all participants.

An in-dwelling catheter will be inserted in a peripheral vein of the lower arm or hand to enable blood sampling. The arm will be put in a hot box to allow collecting arterialized venous blood samples. After taking a baseline blood sample (~5 ml), the predefined meal will be consumed within 10 min. Small arterialized venous blood samples (~3 ml) will subsequently be drawn at 30 minutes and then every 60 minutes after for the duration of the study day. This process will be repeated after consumption of Meal 2 on each study visit. Samples will be collected in predefined tubes (15 blood samples, totaling ~60 ml), plasma/serum separated, aliquoted, and stored at -80 Celsius for later assays and/or sent to a local accredited laboratory. A one-time blooddraw (~12 ml) will be collected for measurement of acute clinical chemistry biomarkers.

- Hemoglobin A1C
- Insulin
- Renal function panel (Alb/BUN/Calcium/CO2/Cl/Creat/Glucose/Phosp/Potassium/Sodium)
- Hepatic function panel (ALT, AST, Alb, Alk Phos, Direct bili, Total Bili, Total protein)
- Lipid panel (Total Cholesterol, HDL Cholesterol, LDL Cholesterol, Triglycerides, VLDL Cholesterol)

- CBC (DIFF/PLT) (Hematocrit, Hemoglobin, MCV, MCH, MCHC, RBC, WBC, Platelet count, and percentage and absolute differential counts)
- hsCRP

In the opposite limb, a commercially-available microdialysis catheter will be placed in the forearm following standard operating procedures developed by the European Academy of Allergy & Clinical Immunology Task Force on Skin Microdialysis. Dialysate will be collected in 60-minute aliquots in microvials for the duration of the study day. Microvials will be weighed before and after sample collection. A syringe filled with perfusate containing a mixture of stable tracer-labeled amino acids and glucose will be infused through the syringe pump at a controlled rate (5 μ l/min; total fluid perfused 4.5 ml).

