12.0 Data and Specimen Banking: Laboratory analysis of samples

The concentrations of amino acids and other parameters (fatty acids, glucose, insulin) will be measured. The plasma metabolite concentrations will be measured using a LC-MS/MS with an

IRB NUMBER: IRB2023-0400F
IRB APPROVAL DATE: 4/10/2024

ABSciex QTRAP 5500 {Engelen, 2013, 445-53}{Jonker, 2014, 211-20}{Luiking, 2015, 57-67} or a Bruker GC with a SCION Triple Quad Mass Spectrometer. The Center for Translational Research in Aging and Longevity (CTRL) at Texas A&M University (TAMU) has all the resources to perform the described experiments.

Banking

Participants can opt-in/out of allowing samples to be stored for future use in consent. Samples will be stored in -80 freezer biobank that is continuously monitored for temperature, has controlled and monitored access. Specimens will be stored for a minimum of 7 years. Only authorized members of the CTRL research group will have access.

13.0 Data and Specimen Management:

The participant's right to confidentiality will be protected at all times and no participant will be identified by name in any publication that results from this research. Participants will be screened in private. Any potentially sensitive information will only be collected in a one-on-one setting. Participants will be informed that this study is also protected under a Certificate of Confidentiality from the National Institutes of Health. The samples will be stored under an identifier, so they are not linked directly to the participant's name. Any personal identifying information that will no longer be used for the research study will immediately be destroyed by the use of an office shredder. All study data collected by the research team, will be recorded on data flow sheets or case report forms (CRFs), and stored in locked file cabinets or databases in a secure area of the PI/Co-I's offices. Each participant will have a binder devoted to filing all pertinent CRFs and all other documents relevant to participation in the study, including printouts of laboratory reports, analytical data (e.g., tracer/tracee ratios, etc.) and any other pertinent information. Any data on a computer will be stored on a secure server with access only to research staff appointed by the PI.

14.0 Provisions to Monitor the Data to Ensure the Safety of Participants:

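### Does the primary endpoint depend on a triglyceride measurement that the laboratory section leaves out?

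*Protocol*

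**What the plan says.** Section 10.0 of the protocol gives one endpoint: prediction models of postprandial plasma glucose in relation to meal composition, assessed by plasma and/or "ISF concentrations of amino acids, glucose, and/or triglycerides". Triglycerides are its only lipid.

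Section 12.0, on laboratory analysis, states: "The concentrations of amino acids and other parameters (fatty acids, glucose, insulin) will be measured". Fatty acids are there; triglycerides are not.

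Section 11.0 names triglycerides once, within the "Lipid panel (Total Cholesterol, HDL Cholesterol, LDL Cholesterol, Triglycerides, VLDL Cholesterol". That panel comes from a separate draw: "A one-time blooddraw (~12 ml) will be collected for measurement of acute clinical chemistry biomarkers". The serial sampling is described apart from it: "Small arterialized venous blood samples (~3 ml) will subsequently be drawn at 30 minutes and then every 60 minutes after". The serial samples are aliquoted and frozen for assays to be done later, or sent to an accredited local laboratory.

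The objective in section 4.0 is wider than any of these lists: "Establish a quantitative relationship between macronutrient intake from fresh meals and the resulting blood and ISF levels of small-molecule metabolites (nutritional biomarkers").

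**The concern.** Fat is one of three macronutrients varied across the eight meals, at 15 g or 40 g. A reader who wants to know which blood marker follows fat intake finds one lipid in the endpoint and another in the laboratory list. The only named triglyceride value comes from one draw with no stated relation to a meal. Read literally, the endpoint's lipid input has no named post-meal measurement. If the serial assay were never run, models using triglycerides could not be fitted. If the team then turned to fatty acids, the lipid predictor would differ from the one the endpoint names.

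**Working it through.** No stated design figure rests on this point, so the check is mainly a comparison of text, with a count of samples to size the assay.

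**1. The two lists side by side**

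| Analyte | Endpoint input (10.0) | Laboratory list (12.0) | One-time clinical chemistry draw (11.0) |
|---|---|---|---|
| Amino acids | yes | yes | no |
| Glucose | yes | yes | yes |
| Triglycerides | yes, joined by and/or | not named | yes |
| Fatty acids | no | yes | no |
| Insulin | no | yes | yes |

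Only the triglyceride row raises a question. Fatty acids and insulin are both measured without being endpoint inputs. That is no defect, because the objective covers small-molecule metabolites generally.

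**2. Can the one-time draw supply the input?** No. It gives one value per participant, against eight meals over four study days. A post-meal triglyceride series has to come from the serial samples.

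**3. Can the serial samples supply it?** Take meals at 0 h and 8 h, with four hours of monitoring after the second (section 11.0: "two per day) and then monitored for four hours after the meal. Meals will be spaced at 8 hours"). Read the schedule as 30 minutes, then each full hour:

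- First meal: 0, 0.5, 1, 2, 3, 4, 5, 6, 7 h = 9 samples.
- Second meal: 8, 8.5, 9, 10, 11, 12 h = 6 samples.
- Total: 9 + 6 = 15, which matches the 15 blood samples stated.

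Reading the times as 0.5, 1.5, 2.5 h and so on gives 9 + 5 = 14, one short of the stated count. Reading the 15 as covering all four days would give 15 / 4 = 3.75 per day, which does not fit the schedule. So 15 per study day is the natural reading. It puts five post-meal samples (0.5, 1, 2, 3, 4 h) inside each four-hour window.

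**4. Size of the assay, if it is run**

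- Per participant: 15 × 4 = 60.
- For the 33 participants needed: 60 × 33 = 1,980.
- For the maximum enrolment of 40: 60 × 40 = 2,400.

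The samples exist in any case; only the determination would be added. The protocol gives no aliquot volumes, so it is an assumption that enough plasma remains from samples of about 3 ml.

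**5. Does anything else in the plan depend on it?** Section 7.0 sizes the study on a 30% difference in protein and carbohydrate amounts, with power 0.8 and significance level 0.05. Fat and triglycerides do not enter. The fat content of each meal is fixed in Table 1 and is known without a lipid assay. The modelled outcome is plasma glucose, which is on the laboratory list.

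**The case for a change.** The strongest case for a change is that an input to the primary endpoint, even an optional one, should have a named measurement. Three points support it. The lipid panel does not explain the omission, because glucose and insulin also appear in the one-time draw and section 12.0 still lists both. Section 12.0 carries no wording that marks its list as illustrative, whereas the questionnaire list in section 11.0 does. And a statistical analysis plan could choose model inputs but would not by itself reconcile two protocol sections.

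The factual part of this stands: the sections do name different lipids, and the single panel value cannot serve. The consequence does not follow. Lacking illustrative wording is not the same as claiming to be complete, and the frozen aliquots leave the assay open. Nor does the gap let the lipid predictor be picked after the data are seen, because section 10.0 already names it. Whatever freedom exists there comes from the and/or wording, which is a separate matter, and the final choice of predictors is commonly left to the analysis plan.

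The possible remedies gain little. Adding triglycerides to section 12.0 mostly writes down an assay that the endpoint already implies. Replacing triglycerides with fatty acids in section 10.0 would be more than editing: it would change an input of the approved primary endpoint to match a laboratory list, and the protocol gives no reason to prefer fatty acids.

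**Conclusion.** No change to the plan follows. The mismatch is a minor omission of laboratory detail affecting one optional input. A team that follows the protocol as written can still reach its primary endpoint from amino acids and glucose, and can assay triglycerides on the stored serial samples if it wants them in the models (about 60 determinations per participant). Fatty acids can stay on the list as an additional measure. The sample size is unaffected, and no bias or loss of power can be computed from the text.

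This rests on three readings: that the and/or in section 10.0 makes triglycerides optional, that the section 12.0 list is not exhaustive, and that enough stored plasma remains for a further assay. Figure 1, the study-day overview, is not shown and may name the assay.

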IRB APPROVAL DATE: 4/10/2024

health monitoring only allow accurate measurements of physical activity and do not provide reliable measurement of macronutrient intake or availability of metabolites after digestion. Invasive blood samples are inconvenient and only periodic. While minimally-invasive wearable probes for tracking glucose trends are emerging (e.g., CGMs), no tools currently exist to provide on-demand monitoring of multiple macronutrient metabolites (e.g., glucose + amino acids). Thus, there is a technology gap that could be filled with multi-analyte sensing devices.

Innovation

Interstitial fluid (ISF) levels of metabolites are hypothesized to have complex but consistent relationship with their levels in blood/plasma, such that knowledge of ISF levels may be used to predict both blood levels and macronutrient amounts. An innovative combination of insertable optical reporters combined with wearable readers and advanced computational methods are proposed to provide continuous/on-demand measurement of these metabolites in ISF and used them as “nutritional biomarkers” to predict macronutrient intake

6.0 Inclusion and Exclusion Criteria:

Recruitment & Screening

Healthy older adults (50-75y; equal gender) with a BMI between 25 and 35 will be recruited from an existing database of CTRAL. In addition, we will recruit older adults that respond to distributed flyers and advertisements in the newspaper and to radio announcements in the community of the College Station/Bryan area. Informed consent will be obtained on the screening day before any study related procedures will be performed. If inclusion/exclusion criteria are met, participants are invited to take part in the study.

Inclusion criteria

- Ability to walk, sit down and stand up independently
- Age 50-75 years old
- Ability to lie in supine or slightly elevated position for approximately 13 hours
- BMI between 25 and 35
- Willingness and ability to comply with the protocol

Exclusion Criteria

- Established diagnosis of malignancy
- Established diagnosis of Insulin or non-Insulin Dependent Diabetes Mellitus
- History of untreated metabolic diseases including hepatic or renal disorder
- Currently on anticoagulants (i.e., warfarin, factor X inhibitors or direct thrombin inhibitors)
- History of deep vein thrombosis, pulmonary embolisms, or known clotting disorders
- Presence of acute illness or metabolically unstable chronic illness
- Recent myocardial infarction (less than 1 year)

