- All experimental procedures will be performed by appropriately trained and credentialed personnel, following Standard Operating Procedures (SOP). The infusion procedure will be monitored by licensed medical personnel and halted if necessary.
- As part of the safety plan for this study, the PI and/or study coordinator will review individual participant records continuously to ensure that appropriate mechanisms to protect the safety of study participants are being followed, that protocol requirements are being adhered to, and that data is accurate, complete, and secure.
- Blood draws: Blood will be withdrawn from a venous line with aseptic technique, which will minimize the risk of infection but will not eliminate it completely. A small volume of saline will be infused during the test days. Participants are not expected to experience any noticeable effects. Expected adverse event due to blood sampling is anemia. Symptoms may include anemia as seen in laboratory tests (low hemoglobin). With the described amount of blood loss the occurrence of anemia is not likely. The hand will be monitored and exposure limited while in a temperature controlled box to minimize risk of scalding. Temperature of the hot box will be monitored and recorded every 2 hours. Cloth or gauze may also be placed over the hand to minimize these risks. The hand may also be removed between blood draws, but must be in the box for 10 minutes prior to the next blood draw.
- Sterile stable isotope solutions will be made as concentrated stock solutions in ready to use working solutions in vials. Sterile compounding of the stable isotope solutions will be completed onsite in United States Pharmacopeia (USP)797 certified cleanroom at the Human Clinical Research Building under the supervision of a licensed pharmacist. Prior

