- All participants will be assigned a unique code corresponding with their enrollment in the study. This code will be used on all documents used to collect and enter data. The link to the code is maintained on secure server separate from the data.
- In the event of an emergency during the test days proper emergency response protocols (calling 9-911 for serious injury or a medical emergency, calling Biosafety/EHS for cleanup assistance or spill team response, calling UPD for incidents in public areas, retrieving AED located in the lab, performing CPR or other First Aid techniques, etc.) will be followed depending on the severity of the emergency.
- If an adverse event occurs, during or subsequent to the study, the nurse and PI will be notified immediately. In case of a serious adverse event also the study physician will be notified immediately. All research staff complete American Heart Association HeartSaver training containing skills for first aid, CPR, and AED.
- Research staff are trained and follow standard operating procedures for all clinical measurements, acute resistance exercise, and endurance exercises. This training provides normal range of various safety measurements as appropriate (e.g., blood pressure, O2 saturation, temperature VAS scale for fatigue and soreness). If measurements are outside normal range, staff immediately inform PI to assess potential participant safety and ability to continue protocol. All measurements and action are recorded in CRF. All staff are made aware of potential adverse events and safety measures enacted during weekly staff meetings.
- The frequency with which all available data and adverse events for completed participants will be reviewed based on actual accrual rates of participants (33% of enrollment needed for completion, or every 6 months, whichever comes first) by (co)PI and study coordinator/ key research staff to ensure safety of participants and integrity of data collected.
- Participants will be given contact numbers and told to contact the research staff if they perceive anything unusual. All adverse events will be recorded in the participant's record file and the (S)AE form of the CRF will be completed. The PI will ensure that the information, including onset, duration and nature of event, severity, and action taken, is captured.
- In case of a serious adverse event the study physician will also be involved in the evaluation and attribution on the risk/benefit ratio.

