- The PI and nurse and if needed other research staff conducting the study will be responsible for evaluating each AE for relationship to the protocol and products, seriousness and expectedness and will determine attribution as well as the impact of the adverse event on the risk/benefit ratio, using the Grading and Attribution Scale as appropriate. Each event is graded according to the following criteria:
 - Mild – transient laboratory test alterations that do not suggest injury; discomfort noted but no disruption of daily activities; no therapy, or only symptomatic therapy required.
 - Moderate – Laboratory test alterations indicating injury without long-term risk, discomfort sufficient to modify normal daily activity, specific therapy required (i.e., more than symptomatic).
 - Serious – laboratory tests indicating a serious health threat or permanent injury, incapacity, inability to work, or to perform normal daily activity, hospitalization required or prolonged, emergency treatment required, life-threatening events, death.
- The attribution scale assesses the relation of the event to the study procedures. The PI and nurse and if needed other research staff conducting the study will judge whether or not an adverse event is:
 - 1) not related;
 - 2) possibly related;
 - 3) probably related;
 - 4) definitely related to the study interventions.

In case of a serious adverse event the study physician will also be involved in the evaluation and attribution on the risk/benefit ratio.

- The PI will report, based on HRP-029 Reportable New Information:
 - any serious adverse events that may be considered unanticipated problems to the IRB within 5 business days of the investigator becoming aware of the event. Unanticipated problems that result in a participant's death or are potentially life-threatening will be reported to the IRB as soon as possible, but no longer than 5 business days. The investigator will report an unanticipated problem to the IRB by completing and submitting Reportable New Information Form.
 - If participants are hospitalized, undergo additional treatments, or die as a result of disease progression, or other age-related conditions they may be excluded from the study after evaluation against study in/exclusion criteria.

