- Health deterioration and hospitalization due to underlying conditions or treatment may be expected events between enrollment and completion of the study. Although the possibility is unlikely due to the strict in- and exclusion criteria and the type of intervention, death and readmission after hospital discharge might occur in these patients related to their underlying condition(s)
- Exposure to low levels of x-ray radiation during DXA scan

17.0 Potential Benefits to Participants:

There are no direct benefits to the study participants.

18.0 Vulnerable Populations:

n/a

19.0 Sharing of Results with Participants:

Results of body composition scan can be shared with participants upon their request. No other research related data will be shared directly with the participants.

20.0 Setting:

IRB NUMBER: IRB2023-0400F
IRB APPROVAL DATE: 4/10/2024

All research activities will take place in private rooms within the CTRAL-Clinical Research Unit (CRU). These spaces are only accessible to trained research staff and other enrolled participants who are accompanied at all times by research staff.

21.0 Resources Available:

The **CTRAL-CRU** consists of 12 overnight stay beds (4 private rooms, 4 semi-private rooms, one 4-bedroom), 4 private exam/procedure rooms, 1 room to measure resting energy expenditure, a nurse station, family waiting room, phlebotomy room, offices, and several storage rooms. Two of the private rooms have bariatric size beds. All rooms in the CTRAL-CRU are stocked with required equipment for safely collecting, processing, and disposing of biohazardous materials. Additionally, each bed has oxygen supply, nurse alarm system, emergency power, internet connection, direct point-to point communication possibility with nursing station, TV/DVD, recliner for (overnight) visitors, personal storage for subjects. CTRAL-CRU has 5 custom made hot-boxes to obtain arterialized-venous blood samplings, automatic and manual B/P Machines, pulse oxygen meter, CPR board, blood glucose glucometers (Accu-Check Aviva), as well as continuous glucose monitor system (Abbott Freestyle Pro), 3 manual wheelchairs and an electric wheelchair. Research nursing staff and study physician are responsible for the medical aspects of the outpatient part of the studies. CTRAL is at the Texas A&M campus and is readily accessible with easy parking for study subjects and staff. Wall mounted storage boxes for sample pick-up by commercial laboratories are also available.

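### Section 19.0 bars direct sharing of all research results except the DXA scan and, on its plain reading, makes no exception for clinically significant results from the section 11.0 laboratory panels

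*Protocol*

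**What the plan says.** Section 19.0 has two sentences. The first permits one result: "Results of body composition scan can be shared with participants upon their request". The second closes the rest: "No other research related data will be shared directly with the participants".

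Section 11.0 describes the scan together with the screening visit: "We also will perform Dual-energy X-ray absorptiometry (DXA) to measure body composition". The same section orders the clinical laboratory work: "A one-time blooddraw (~12 ml) will be collected for measurement of acute clinical chemistry biomarkers". It lists HbA1c, insulin, renal, hepatic and lipid panels, a CBC with differential, and hsCRP.

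Section 6.0 excludes "Established diagnosis of Insulin or non-Insulin Dependent Diabetes Mellitus". It also lets the PI or nurse exclude a person for any other condition found at the screening visit that would interfere with the study or with safety.

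Section 14.0 says what staff do with abnormal values: "If measurements are outside normal range, staff immediately inform PI to assess potential participant safety and ability to continue protocol". Its adverse event scale includes, in the most severe grade, "laboratory tests indicating a serious health threat or permanent injury". It also makes the investigator responsible for deciding what safety requires. Section 21.0 gives the research nurses and study physician a general medical role.

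**The concern.** The protocol orders routine clinical tests in adults aged 50 to 75 with a BMI of 25 to 35, and then adopts a rule that, read plainly, keeps those results from them. Tests of this kind can reveal a condition that the participant does not know about. A diabetic-range HbA1c, a raised creatinine, raised liver enzymes or a low haemoglobin is seldom an emergency, but each is something a person would normally want confirmed and followed in ordinary care.

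This is not a detail that a statistical analysis plan would supply. Section 19.0 sets a rule, and the question is whether that rule is drawn too widely. Only participant welfare is at stake.

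**Working it through.** No arithmetic applies, so the check sets the relevant sections against each other.

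1. **What the bar covers.** Section 19.0 names the DXA result and then refers to *other* research related data. The scan, although described with the screening visit, is thus treated as research related data. The clinical panels stand in the same section 11.0 as study procedures, and nothing takes them out of the rule. The plain reading is that they are covered.

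2. **What the panels can show.** Section 11.0 lists seven test groups. The point relies on five (HbA1c, renal, hepatic, lipid, CBC) and leaves out insulin and hsCRP: 7 − 2 = 5. This describes the scope of the tests; it does not count affected results.

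3. **Whether an unrecognised abnormality can occur in a participant.** The diabetes criterion turns on an established diagnosis, so it does not by itself catch an undiagnosed case. The criterion on conditions found at screening could catch one if the result is known by then. The text of section 11.0 does not date the one-time draw, and the study-day figure is not visible. In either case, excluding a person is a different step from telling them the result, and section 6.0 provides only for the former.

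4. **Where abnormal values go.**
   - Section 14.0, out-of-range measurements: to the PI. The examples given are blood pressure, oxygen saturation, temperature and fatigue or soreness scales.
   - Section 14.0, adverse events: graded by the PI and nurse, with the study physician added if serious. An abnormality that was present before the study is not clearly an adverse event.
   - Section 14.0, investigator's safety responsibility: general, with no mention of laboratory results.
   - Section 21.0: a medical role for nurses and physician, with no disclosure step.

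   None of these provides for telling the participant, and none qualifies section 19.0.

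5. **Whether investigator discretion fills the gap.** Section 14.0 requires IRB review before any unapproved action, except to remove an apparent immediate hazard. It also requires failures to follow the protocol to be reported within 5 business days. If section 19.0 is read plainly, disclosing a panel result could count as such an action. The exception for immediate hazards does not usually fit a diabetic-range HbA1c or a raised creatinine. Discretion is therefore weakest for the non-urgent results at issue.

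**The case against.** The strongest reply is that non-disclosure follows only if three open questions all go one way: the panels are research related data, *directly* also closes a route through a physician or referral, and the consent form is silent.

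- **The panels.** Section 11.0 calls them clinical chemistry and lists them apart from the serial metabolite samples, so the first question is arguable. They are nevertheless study procedures with no carve-out, and the DXA comparison points towards coverage.
- **The word *directly*.** It may well leave a clinician's route open. The protocol describes none, so staff would have to infer one from an adverb.
- **Consent.** The consent pages are not part of the text available here, and their content cannot be counted as missing. This limits the claim. If they do promise disclosure, section 19.0 as plainly read would conflict with them and would still need correcting.
- **Adverse event handling.** The moderate grade includes events that need specific therapy, which could hardly be given without the participant's knowledge. That helps for events arising in the study, but not clearly for abnormalities already present.

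Three stronger readings are tempting and are not supported:

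- A reader might infer that significant results will definitely be withheld. The uncertainty over *directly* and over consent rules that out.
- A reader might infer that an established diagnosis is the only barrier to enrolling someone with diabetes. The further section 6.0 criterion on conditions found at screening shows otherwise.
- A reader might take the section 14.0 remark on anaemia as evidence that the protocol foresees incidental panel findings. That remark concerns anaemia caused by study blood sampling, which the protocol considers unlikely.

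**Conclusion.** The point holds as a risk to participant welfare. Section 19.0 exempts one result and, on its plain reading, bars direct sharing of the section 11.0 clinical panels without an exception for clinically significant values. No visible part of the protocol provides for telling the participant, so a significant but non-urgent result may not reach them.

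This rests on two assumptions: that the panels count as research related data, and that neither the reading of *directly* nor the unseen consent wording supplies a route. Confidence is therefore moderate. The size is qualitative, because the documents give no frequency of abnormal results. No endpoint, power calculation or analysis is affected. The change is worth making because it is cheap and removes the dependence on interpretation.

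**What to change.** Limit the no-sharing sentence in section 19.0 to the exploratory metabolite assays in plasma and dialysate. Then add a sentence such as: *Section 11.0 clinical laboratory results judged clinically significant by the study physician will be communicated to the participant and, with the participant's permission, to the participant's own doctor.* Align the consent wording if it differs.

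The cost is an IRB amendment and a little review time from the study physician, who is already part of the protocol. Visits, samples, endpoints and analysis stay as they are.
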